#### 4.9. Visits 10 – 12: Follow-Up Visits

These visits begin approximately 3 months after Visit #6.

The purpose of the follow-up visits is to monitor for symptom changes, report any complications and to optimize programming if necessary. Subjects will come in at 3 months after implantation of the neurostimulator and then every 3 months for Visits 11 and 12 (6 and 9 months after implantation of the neurostimulator, respectively). The study neurologist experienced in programming in conjunction with one of the study psychiatrists will use TS symptom scales (especially the YGTSS), acute changes in other comorbid conditions (OCD/ADHD), acute changes in depression or anxiety symptoms, and/or appearance of adverse events deemed likely to be related to DBS to optimize programming at all subsequent follow-up visits.

The following assessments will be conducted:

- Programming Form
- New/changed adverse events
- Record changes in concomitant medications
- TS symptom scales (YGTSS, YBOCS, WHO ASRS)

Date: 2/24/2021

Principal Investigator: [name], PhD

Application Number: NA\_00073086

- Ham-D, BAI, YMRS (Beck Youth Inventory for ages 15-17)
- GAF
- CSSS at alternating visits.
- Neurocognitive battery (for Visit #11 as per Visit #1)

At the conclusion of this visit, the subject will be given an appointment card for the next study visit, which is the final study visit.

#### **4.10. Visit 13 – Study Completion (or Early Termination Visit)**

This visit is approximately 4 months after Visit #12.

The purpose of this last visit is to monitor for symptom changes, report any complications and to optimize programming if necessary. Subjects will come in at 4 months after the last visit (12 months after implantation of the neurostimulator). The study neurologist experienced in programming in conjunction with one of the study psychiatrists will use TS symptom scales (YGTSS, YBOCS, and the WHO Adult ADHD Self-Report Scale), acute changes in depression or anxiety symptoms, and appearance of adverse events deemed likely to be related to DBS to optimize programming at all subsequent follow-up visits.

The following assessments will be conducted at study completion (or if the subject is early terminated from the study for any reason):

- Programming Form
- New/changed adverse events
- Record changes in concomitant medications
- TS symptom scales (YGTSS, YBOCS, and the WHO ASRS)
- Ham-D, BAI, YMRS (Beck Youth Inventory for ages 15-17)
- GAF
- Neurocognitive battery (as per Visit #1)

At the conclusion of this visit, the subject will be discharged from the study and will continue standard clinical care for patients who undergo DBS procedures. The patient will continue to meet with the study physicians. If symptom improvement has been observed with DBS, the patient will continue standard of care for DBS. If symptom improvement has not been observed, the subject can opt to have the stimulation device turned off.

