The subject will come in for four further follow-up visits weekly after the initial programming session (Visit #6). The study neurologist experienced in programming in conjunction with one of the study psychiatrists will use TS symptom scales (especially YGTSS), acute changes in OCD or ADHD symptoms, acute changes in depression or anxiety symptoms, and/or appearance of adverse events deemed likely to be related to DBS to optimize programming at all subsequent follow-up visits.

The following assessments will be conducted:

- Programming Form
- New/changed adverse events
- Record changes in concomitant medications
- TS symptom scales ( YGTSS, YBOCS, WHO ASRS)
- Ham-D, BAI, and YMRS for depression, anxiety, and/or mania symptoms (Beck Youth Inventory for ages 15-17)
- CSSS at alternating visits.
- Global Assessment of Function Scale (GAF)
- Neurocognitive battery (as per Visit #1)

At the conclusion of this visit, the subject will be given an appointment card for the next study visit.

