#### **4.11. Early Discontinuation/Treatment Failure**

Subjects may choose to discontinue study participation at any time, for any reason, specified or unspecified, and without prejudice. If a subject chooses to discontinue early after implantation of the DBS device, the investigator must request that the subject return to the clinic within 24 hours and complete the assessments for early termination described in Section 4.10. The Investigator will have the subject's DBS device turned off and request that the subject continue to come in for monitoring visits to complete safety assessments. Subjects who are determined to be treatment failures, as defined by having no improvement in tic symptoms (as scored with the YGTSS) will be offered the option to have the DBS device turned off after a period of 3 months to allow suitable time for appearance of clinical improvement. Subjects who experience a worsening of TS, OCD, ADHD, depression, or anxiety symptoms that persists for 4 weeks will have the device turned off. The Investigator must request that such subjects also return to the clinic

Date: 2/24/2021

Principal Investigator: [name], PhD

Application Number: NA\_00073086

within 24 hours and complete the assessments for early termination described in Section 4.10 as well as continue to come in for monitoring visits to complete safety assessments.

All subjects must be educated that although the DBS device will be turned off in the event of discontinuation from the study, the DBS device will **not** be removed, as the risk of such a procedure outweighs any perceived benefits.

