#### 4.12. Table of Visits and Testing

Visit #	Approx. Week #	TS symptom scales	Other psych testing	Surgical procedures	Adverse event monitoring	IPG programming	Medication change monitoring	Urine tox
1	0	DSM-IV SCID, YGTSS,YBOCS, WHO ASRS	Ham-D, BAI,GAF, CSSS,YMRS,NCOG	NA	NA	NA	medications recorded	yes
2	2	DSM-IV SCID, YGTSS,YBOCS, WHO ASRS	Ham-D, BAI,GAF, YMRS	NA	NA	NA	yes	yes
3	4	YGTSS,YBOCS, WHO ASRS	Ham-D, BAI, CSSS,YMRS	NA	NA	NA	yes	yes
4	7	NA	NA	Implantation of DBS leads	yes	NA	NA	NA
5	8	YGTSS,YBOCS, WHO ASRS	Ham-D, BAI, YMRS	Implantation of IPG	yes	yes	yes	NA
6	11	YGTSS,YBOCS, WHO ASRS	Ham-D, BAI,GAF, CSSS,YMRS,NCOG	NA	yes	yes	yes	NA
7	12	YGTSS,YBOCS, WHO ASRS	Ham-D, BAI,GAF, YMRS,NCOG	NA	yes	yes	yes	NA
8	13	YGTSS,YBOCS, ADHD	Ham-D, BAI,GAF, CSSS,YMRS,NCOG	NA	yes	yes	yes	NA
9	14	YGTSS,YBOCS, WHO ASRS	Ham-D, BAI,GAF, YMRS,NCOG	NA	yes	yes	yes	NA
10	23	YGTSS,YBOCS, WHO ASRS	Ham-D, BAI,GAF, CSSS,YMRS	NA	yes	yes	yes	NA
11	35	YGTSS,YBOCS, WHO ASRS	Ham-D, BAI,GAF, YMRS,NCOG	NA	yes	yes	yes	NA
12	47	YGTSS,YBOCS, WHO ASRS	Ham-D, BAI,GAF, CSSS,YMRS	NA	yes	yes	yes	NA
13	62	YGTSS,YBOCS, WHO ASRS	Ham-D, BAI,GAF, YMRS,NCOG	NA	yes	yes	yes	NA

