#### 4.13. Unscheduled Visits

Subjects may telephone the study team to request additional visits if he/she experiences new adverse events. The subject will be asked to come to the study site within 24 hours (or to go their local emergency room if it is assessed to be serious by an Investigator).

The following assessments will be performed:

- New/changed adverse events

Date: 2/24/2021  
Principal Investigator: [name], PhD  
Application Number: NA\_ 00073086

- Record changes in concomitant medications
- TS symptom scales (YGTSS, YBOCS, and the WHO ASRS)
- Ham-D, BAI, YMRS, and CSSS (Beck Youth Inventory for ages 15-17)

Unscheduled visits for assessment and treatment of potential DBS-related adverse events are allowed throughout the study.

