### **5.3. Exclusion Criteria**

Date: 2/24/2021

Principal Investigator: [name], PhD

Application Number: NA\_00073086

1. Subject has a positive urine drug screen at any of the three Baseline Visits.
2. Subject had major surgery within three months prior to Baseline Visit 1 or has other surgery planned during the proposed study period.
3. Subject is determined by medical consultant to have medical contraindications to undergoing surgery.
4. Subject is pregnant or breast-feeding.
5. Subject has a history of alcohol or drug abuse within the past 6 months and/or dependence within the past year.
6. Subject has a medical illness/condition, and/or abnormal diagnostic finding that would interfere with the completion of the study, confound the results of the study, or pose risk to the patient.
7. Subject has an untreated or uncontrolled Axis I disorder or other major psychiatric disorder including major depression, bipolar disorder, or schizophrenia as determined by the screening psychiatrist.
8. Subject has either a current or past history of suicidal plan and/or intent.
9. Subject has a tic disorder or other movement disorder attributable to another medical, neurological, or psychiatric disorder other than Tourette Syndrome.
10. Subject has a drug-induced tic disorder.
11. Subject has significant psychosocial factors that might increase the risk of the DBS procedure or complicate recovery and outcome assessments. (Examples include – history of noncompliance with previous medical and psychosocial treatments, multiple failed medication treatments of inadequate dose or duration, a history of multiple other surgical procedures with poor outcome, unexplained medical history gaps, or pending lawsuits or other legal action.)
12. Subject has metal in the head or any other type of implanted stimulator (i.e. cardiac pacemaker, deep brain stimulator for a different disease, spinal cord stimulator, cochlear implant, vagus nerve stimulator, etc.).
13. Subject has participated in another investigational drug trial or therapeutic trial within 30 days of Baseline Visit 1.
14. Subject has a diagnosis of intellectual disability with documented IQ<70.
15. Subject has a neurological condition, or a history of traumatic brain injury associated with loss of consciousness of > 1 hour and/or intracranial/epidural/subdural bleeding.

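### The early-termination assessment list in Section 4.10 omits the CSSS, so a subject switched off for persistent worsening is recalled without the protocol's suicidality scale

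*Combined protocol and SAP*

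**What the plan says.** Section 4.10 defines the Visit 13 assessments and states when they apply: "The following assessments will be conducted at study completion (or if the subject is early terminated from the study for any reason". The psychiatric scales on the list are "Ham-D, BAI, YMRS (Beck Youth Inventory for ages 15-17". The other entries are the programming form, adverse events, medication changes, the three TS, OCD and ADHD scales, the GAF and the neurocognitive battery. The CSSS is on no line. Row 13 of Table 4.12 agrees; its entry for other psychiatric testing is "Ham-D, BAI,GAF, YMRS,NCOG".

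Section 4.11 routes two groups to this list, each to be asked back within 24 hours. One is subjects who choose to stop after implantation. The other is defined by a clinical trigger: "Subjects who experience a worsening of TS, OCD, ADHD, depression, or anxiety symptoms that persists for 4 weeks will have the device turned off". The second group must "complete the assessments for early termination described in Section 4.10 as well as continue to come in for monitoring visits to complete safety assessments". The content of those later monitoring visits is not given.

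Elsewhere the CSSS is present. Section 4.8 lists "CSSS at alternating visits", and Sections 4.9 and 4.14 do the same. Section 4.13, for visits that a subject requests because of new adverse events, lists "Ham-D, BAI, YMRS, and CSSS (Beck Youth Inventory for ages 15-17", with no alternation. Section 8.4 identifies the CSSS as the means of assessing suicidal thoughts.

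**The concern.** An early termination is triggered by an event. One of the named events is depression that has worsened and stayed worse for four weeks, which is a moment when a suicidality scale is most wanted. The protocol's other event-triggered visit, in Section 4.13, includes that scale. A subject who telephones about a new adverse event is therefore listed for the CSSS, while a subject recalled because persistent worsening has led to switch-off is not.

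Safety is one of the two primary objectives (Section 2.1), and Section 8.3 gives depression and suicidal ideation as an example of a therapy-related event. The CSSS is taken at baseline Visits 1 and 3, so an exit value could be set against the same subject's own pre-operative values. Without it, suicidality at exit rests on adverse event reporting and on general mood scales.

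**Working it through.** The plan states no figure on this point. The check compares the assessment lists and then subtracts week numbers.

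**Lists compared.**

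| Section | Visit type | CSSS listed |
|---|---|---|
| 4.8 | Visits 6-9 | Yes, alternating |
| 4.9 | Visits 10-12 | Yes, alternating |
| 4.10 | Visit 13, or early termination | No |
| 4.13 | Unscheduled, for adverse events | Yes, every time |
| 4.14 | Long-term follow-up | Yes, alternating |

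Section 4.9 lists eight items and Section 4.10 lists seven. The one not carried over is the CSSS. (The pre-programming list in Section 4.7, for Visit 5, also has no CSSS, so 4.10 is not the only post-operative list without it.)

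**Does alternation explain the omission?** Table 4.12 places the post-operative CSSS at Visits 6, 8, 10 and 12. Visits 7, 9, 11 and 13 have none, so its absence at a scheduled Visit 13 fits the pattern. Early termination has no place in that sequence, because it can fall in any week. Alternation gives no reason for omitting the CSSS there.

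**Age of the last planned CSSS.** From Table 4.12, the CSSS is planned at Weeks 0, 4, 11, 13, 23 and 47 (Visits 1, 3, 6, 8, 10 and 12). Lead implantation is at Week 7 and Visit 13 at Week 62. For a termination in week t, the age is t minus the most recent CSSS week. The largest age in each interval after implantation is:

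- Weeks 7 to 11: 11 − 4 = 7 weeks
- Weeks 11 to 13: 13 − 11 = 2 weeks
- Weeks 13 to 23: 23 − 13 = 10 weeks
- Weeks 23 to 47: 47 − 23 = 24 weeks
- Weeks 47 to 62: 62 − 47 = 15 weeks

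The maximum is just under 24 weeks, for a termination shortly before Visit 12. A subject who completes at Visit 13 had the last planned CSSS 15 weeks earlier. These are gaps in the planned schedule. A Section 4.13 visit in the interval would shorten them.

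**The case against.** **The unscheduled visit may already cover it.** Section 7.3 counts worsening of a pre-existing symptom as an adverse event, so worsened depression qualifies. After Week 14 the scheduled visits are at Weeks 23, 35, 47 and 62, which is 9, 12, 12 and 15 weeks apart. The team will often learn of a four-week worsening because the subject makes contact, and a Section 4.13 visit then brings a CSSS. This stands as a real mitigation, but it does not guarantee the scale: a 4.13 visit depends on the subject's request, and the 4.11 recall invokes the 4.10 list instead. For the same reason, a reader might count the weeks in which the last planned CSSS predates a four-week worsening and treat that share as the chance that a worsening subject lacks a recent CSSS. The documents do not support this. It is a calendar share that ignores 4.13 contacts and weights all weeks equally.

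**Mood is still assessed at exit.** Adverse events, Ham-D, BAI and YMRS are collected, with the Beck Youth Inventory replacing Ham-D and BAI at ages 15-17, and Section 4.10 involves a study psychiatrist. Section 8.4 also requires possible threats of suicide to be disclosed, whatever the CSSS shows. This stands and limits the loss. Yet Section 4.13 lists the same mood scales and still adds the CSSS, so the protocol does not treat them as a substitute.

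**No planned analysis uses the CSSS.** Section 7 defines no CSSS endpoint or threshold, and Section 7.3 assesses safety through adverse events. This stands: no specified analysis loses an input.

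**Later monitoring visits follow switch-off.** They do, but their content is undefined and they come after the exit assessment.

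**Conclusion.** The omission is confirmed by the text and matters at early termination. A subject who discontinues, or who is switched off after four weeks of worsening, is recalled to a list without the CSSS, and the last planned one may be almost 24 weeks old. The figure assumes that visits keep to the approximate weeks of Table 4.12 and that no unscheduled visit intervened. What is lost is the standardised suicidality measure at exit, and nothing wider. This is a cheap improvement and does not undermine the trial's safety assessment.

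Three stronger readings are tempting and are not supported:

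- A reader might infer that every subject starts free of suicidality, so that any exit finding would be new. Exclusion criterion 8 reads "Subject has either a current or past history of suicidal plan and/or intent". It does not name ideation, so an enrolled subject may have ideation at baseline. The comparison is with the subject's own Visit 1 and 3 values.
- A reader might infer that the missing CSSS at completion is also a defect. Visit 12 has it and Visit 13 does not, as the alternation implies.
- A reader might infer that the stopping rules cannot detect suicidal ideation, or will undercount it. Section 7.5 does not require a CSSS to establish ideation, which can also be recorded as an adverse event. Nothing in the documents allows an undercount to be estimated among 10 subjects.

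**What to change.** In Section 4.10, state that the CSSS is added whenever the list is used for early termination, and add a matching note to Table 4.12. The references to 4.10 in Section 4.11 then carry the change without further editing. Collecting it at the scheduled Visit 13 as well is optional; it would give a 12-month value but is not needed to close the gap.

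The cost is one extra administration, per early-terminating subject, of a scale the study team already uses, at a visit that already takes place.

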#### **4.11. Early Discontinuation/Treatment Failure**

Subjects may choose to discontinue study participation at any time, for any reason, specified or unspecified, and without prejudice. If a subject chooses to discontinue early after implantation of the DBS device, the investigator must request that the subject return to the clinic within 24 hours and complete the assessments for early termination described in Section 4.10. The Investigator will have the subject's DBS device turned off and request that the subject continue to come in for monitoring visits to complete safety assessments. Subjects who are determined to be treatment failures, as defined by having no improvement in tic symptoms (as scored with the YGTSS) will be offered the option to have the DBS device turned off after a period of 3 months to allow suitable time for appearance of clinical improvement. Subjects who experience a worsening of TS, OCD, ADHD, depression, or anxiety symptoms that persists for 4 weeks will have the device turned off. The Investigator must request that such subjects also return to the clinic

Date: 2/24/2021

Principal Investigator: [name], PhD

Application Number: NA\_00073086

within 24 hours and complete the assessments for early termination described in Section 4.10 as well as continue to come in for monitoring visits to complete safety assessments.

All subjects must be educated that although the DBS device will be turned off in the event of discontinuation from the study, the DBS device will **not** be removed, as the risk of such a procedure outweighs any perceived benefits.

#### 4.12. Table of Visits and Testing

Visit #	Approx. Week #	TS symptom scales	Other psych testing	Surgical procedures	Adverse event monitoring	IPG programming	Medication change monitoring	Urine tox
1	0	DSM-IV SCID, YGTSS,YBOCS, WHO ASRS	Ham-D, BAI,GAF, CSSS,YMRS,NCOG	NA	NA	NA	medications recorded	yes
2	2	DSM-IV SCID, YGTSS,YBOCS, WHO ASRS	Ham-D, BAI,GAF, YMRS	NA	NA	NA	yes	yes
3	4	YGTSS,YBOCS, WHO ASRS	Ham-D, BAI, CSSS,YMRS	NA	NA	NA	yes	yes
4	7	NA	NA	Implantation of DBS leads	yes	NA	NA	NA
5	8	YGTSS,YBOCS, WHO ASRS	Ham-D, BAI, YMRS	Implantation of IPG	yes	yes	yes	NA
6	11	YGTSS,YBOCS, WHO ASRS	Ham-D, BAI,GAF, CSSS,YMRS,NCOG	NA	yes	yes	yes	NA
7	12	YGTSS,YBOCS, WHO ASRS	Ham-D, BAI,GAF, YMRS,NCOG	NA	yes	yes	yes	NA
8	13	YGTSS,YBOCS, ADHD	Ham-D, BAI,GAF, CSSS,YMRS,NCOG	NA	yes	yes	yes	NA
9	14	YGTSS,YBOCS, WHO ASRS	Ham-D, BAI,GAF, YMRS,NCOG	NA	yes	yes	yes	NA
10	23	YGTSS,YBOCS, WHO ASRS	Ham-D, BAI,GAF, CSSS,YMRS	NA	yes	yes	yes	NA
11	35	YGTSS,YBOCS, WHO ASRS	Ham-D, BAI,GAF, YMRS,NCOG	NA	yes	yes	yes	NA
12	47	YGTSS,YBOCS, WHO ASRS	Ham-D, BAI,GAF, CSSS,YMRS	NA	yes	yes	yes	NA
13	62	YGTSS,YBOCS, WHO ASRS	Ham-D, BAI,GAF, YMRS,NCOG	NA	yes	yes	yes	NA

#### 4.13. Unscheduled Visits

Subjects may telephone the study team to request additional visits if he/she experiences new adverse events. The subject will be asked to come to the study site within 24 hours (or to go their local emergency room if it is assessed to be serious by an Investigator).

The following assessments will be performed:

- New/changed adverse events

Date: 2/24/2021  
Principal Investigator: [name], PhD  
Application Number: NA\_ 00073086

- Record changes in concomitant medications
- TS symptom scales (YGTSS, YBOCS, and the WHO ASRS)
- Ham-D, BAI, YMRS, and CSSS (Beck Youth Inventory for ages 15-17)

Unscheduled visits for assessment and treatment of potential DBS-related adverse events are allowed throughout the study.

#### **4.14 Long-Term Follow-Up Visits**

The purpose of the long-term follow-up visits is to monitor for additional symptom changes, report any complications and to optimize programming if necessary over the lifetime of the implanted system. Subjects will come in at roughly 6 month intervals for two years after Visit #13, and then annually after that. The study neurologist experienced in programming in conjunction with one of the study psychiatrists will use TS symptom scales (especially the YGTSS), acute changes in other comorbid conditions (OCD/ADHD), acute changes in depression or anxiety symptoms, and/or appearance of adverse events deemed likely to be related to DBS to optimize programming at all subsequent follow-up visits. These assessments will occur until the subject no longer wants to participate, or until the device is removed due to a complication or wish of the subject, or until the device generator depletes and the subject no longer wishes to have it replaced.

Replacements for the IPG will be performed when the cell is depleted as assessed during follow-up visits or for changes in symptoms. The first cell implanted at Visit #5 will be the Activa PC (standard cell). Either the Activa PC (standard cell) or the Activa RC (rechargeable system) will be offered at the times of IPG replacement subsequent to this, pending the subject's preference and willingness to participate in the recharging process. The RC system will be discussed with the subject particularly in cases where the lifetime of the prior IPG was less than 2 years.

The following assessments will be conducted:

- Programming Form
- New/changed adverse events
- Record changes in concomitant medications
- TS symptom scales (YGTSS, YBOCS, WHO ASRS)
- Ham-D, BAI, YMRS (Beck Youth Inventory for ages 15-17)
- GAF
- CSSS at alternating visits.
- Neurocognitive battery if suggested for any reason by one of the study neurologists or psychiatrists

#### **4.15 Covid19 Related Protocol Changes**

We are modifying our protocol (summarized below) to minimize risk to participants and study team members by limiting in-person interaction wherever possible.

Date: 2/24/2021  
Principal Investigator: [name], PhD  
Application Number: NA\_ 00073086

#### Preoperative evaluation:

Please note that for this research study, all visits taking place related to placement and maintenance of this implanted neuromodulation system are covered under an FDA Investigational Device Exemption #G120131. Preoperative visits will take place via telemedicine when possible with both the referring neurologist at Johns Hopkins and the operative neurosurgeon. For the preoperative rating scales for the characterization of Tourette Syndrome, in person clinic visits with the multidisciplinary movement disorder team at Johns Hopkins will take place for evaluation. These in person visits will take place at the Johns Hopkins Outpatient Center (JHOC), and will follow current protocols for wearing masks and face shields in the clinic spaces. Evaluated subjects will also be required to wear masks. Similar procedures will be performed by the Neuropsychology Team in the Meyer 2 exam area for the required preoperative neuropsychological testing.

